9.7 Sample Size Determination

- The metric-wise sample size calculation is provided in the table below on alpha as 0.05 and power of 80% for the one-tail test at enrollment ratio = 1.
- While we are conducting the power analysis and sample size calculation based on several variables (outcomes) of interest, the sample size was computed separately for each parameter in the study and the greatest is used to obtain sample size.
- The analysis (detailed below in table) showed that sample of size of 102 is powerful enough for the analysis to cover 100% of primary and secondary metrics.
- Now since we believe that the long follow-up duration of 6 months for our trial will lead to around 30% drop-offs, we decided a final sample size of 146 (73 control, 73 test).

- So even if get 30% or 44 participants drop off we end up with final sample set of 102 (51 control, 51 test) and would be able to come to statistically significant effects ($p < 0.05$) with respect to 100% of primary and secondary metrics.

Metric Segment	Sub Metric	Control Data	Test Data	Assumed Variance	Sample Size
Primary Outcome / Concerns					
Quality of Life Improvement	QoLS Score (FACT-G)	70	85	Variance of 20	42 (21 Control, 21 Test)
Secondary Outcome / Concerns					
Presenteeism	Attitude towards work	2	4	Variance of 1.5	16 (8 Control, 8 Test)
	Employee Performance	0.6	0.7	Variance of 20%	102 (51 Control, 51 Test)
Absenteeism	Working Hours	30	40	Variance of 10	28 (14 Control, 14 Test)
	Vacation Days	0.5	0.3	Variance of 0.15	16 (8 Control, 8 Test)
Exploratory Outcomes					
Cancer Care	Cancer Progression Status	0.85	0.88	Variance of 0.04	46 (23 Control, 23 Test)

	Cancer recurrence status	0.3	0.21	Variance of 10%	32 (16 Control, 16 Test)
Medical Expenditure	Total Healthcare Expenditure (Planned + Unplanned)	10000	8000	Variance of 4000	102 (51 Control, 51 Test)
	No of Urgent Care Visits	3	2.5	Variance of 0.5	28 (14 Control, 14 Test)
	No of ED Visits	5	3.45	Variance of 0.8	10 (5 Control, 5 Test)
	No of unplanned outpatient/office visits (other than ED)	4.28	3.5	Variance of 0.8	28 (14 Control, 14 Test)
	Unplanned Hospitalisations	5	4	Variance of 0.8	18 (9 Control, 9 Test)
	Length of hospital stay	3	2	Variance of 0.8	18 (9 Control, 9 Test)
	No of planned outpatient visits	2	1.8	Variance of 0.3	58 (29 Control, 29 Test)
	No of planned hospital visits	1.25	1	Variance of 0.1	10 (5 Control, 5 Test)
	Length of hospital stay	3	2	Variance of 0.8	18 (9 Control, 9 Test)

Total Prescription Medicine Expenditure	1000	950	Variance of 80	80 (40 Control, 40 Test)
---	------	-----	----------------	--------------------------

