- Multivariate imputation by chained equation (MICE) will be used, i.e., filling the missing data multiple times based on the effect from other covariates by constructing a multivariate regression model. MI is superior to single imputation, as it accounts for the uncertainty of missing values in a more robust way. The number of imputations will be 10, i.e., 10 datasets with imputed data will be created. Each imputed dataset gives a point estimate of the regression coefficients as well as its standard deviation, which will be combined across the 10 datasets to obtain the final estimate and their 95% CIs.
- MICE is flexible and can accommodate variables of different types, as well as complexities such as bounded scales or survey skip patterns, making it well-suited for patient-reported outcomes like QoLS.

- **Sensitivity Analysis**

- To complement our intention-to-treat (ITT) analysis, a per-protocol analysis will be performed, including only participants who fully adhered to the intervention, to explore the effect of adherence on QoLS improvement.

- **Supplementary Analysis**

- Efficacy Analysis: survivors in the treatment and control group will be compared for the outcome variables. The comparison will be evaluated based on both SMD and P value. SMD greater than 0.2 will be considered as acceptable differences (section 3.3 indicated the definition of SMD). Descriptive statistics will be compared between treatment groups and control groups, and P values will be calculated using ANOVA tests comparing means of continuous variables, Brown-Mood test to compare the medians, and Chi-Square tests for binary and categorical variables. The differences will be considered as statistically significant within 95% confidence interval, i.e., P value less than 0.05.

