9.6 Interim Analyses

- Interim analyses are planned to evaluate the primary and secondary objectives' safety and efficacy data. These analyses may also explore data trends that could necessitate adjustments to the trial conduct.
- Statistical Methods:
 - The interim analyses will employ group sequential testing methods with an O'Brien-Fleming spending function to rigorously control the type I error rate across multiple looks at the data.
- Execution:
 - The analyses will be performed by an independent biostatistician from the trial investigators to maintain objectivity.
- Timing and Triggers
 - Scheduled Interim Analyses: Interim analyses are planned at 3 months, 6 months and 12 months of trial commencement.

- Ad Hoc Requests: Additional interim analyses may be conducted at the request of the Trial Monitoring Committee, particularly if unexpected safety concerns arise.
- Decision Criteria and Oversight
 - Decision Criteria: The criteria for early stopping or trial adaptation include a pre-specified boundary for efficacy (significant improvement in Quality of Life Scores or improvement in health outcomes) or safety concerns (unacceptable adverse events rate).
 - The Trial Monitoring Committee will oversee the interim analyses, reviewing the results to make recommendations on continuing, stopping, or modifying the trial.
 - Blinding Integrity: Individuals analyzing the data may have access to unblinded data; however, measures will be taken to ensure that the trial team remains blinded to maintain the integrity of the trial implementation.
 - Authority to Stop or Modify: The ultimate authority to stop or modify the trial rests with the TMC, in consultation with the principal investigator and the sponsor, based on the interim findings and established stopping guidelines.

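### Section 9.7 sizes every metric for a one-tailed 5% test, but the significance criterion in Section 9.2 matches a two-sided 5% test; on that criterion the rows that set the sample size have about 70% power, not 80%

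*Protocol*

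**What the plan says.** **Sizing.** Section 9.7 of the Protocol computes each row "on alpha as 0.05 and power of 80% for the one-tail test at enrollment ratio = 1", and the Combined protocol and SAP does the same. The rule for the total is that "the sample size was computed separately for each parameter in the study and the greatest is used to obtain sample size". The largest rows need 51 per arm, and the text concludes that a "sample of size of 102 is powerful enough for the analysis to cover 100% of primary and secondary metrics". Allowing for 30% dropout gives 146 randomised. Section 9.7 does not mention the interim looks.

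**Significance criterion.** In the Protocol, Section 9.2 takes the primary FACT-G analysis from a mixed model for repeated measures, judges covariate effects by P value at the 95% level, and reports 95% intervals after multiple imputation. Under Supplementary Analysis it compares outcome variables by ANOVA, Brown-Mood and chi-square tests and adds: "The differences will be considered as statistically significant within 95% confidence interval, i.e., P value less than 0.05". Section 9.2 of the Combined document repeats these rules, with a generalised linear model for expenditure as the primary analysis.

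**Hypotheses.** The alternatives in 9.2 and 9.3 are worded in one direction (improvement or reduction). Section 9.3 gives the presenteeism outcomes mixed-effects models, with no alpha, sidedness or interval level. Neither document uses the term two-sided or two-tailed.

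**Interim looks.** Section 9.6 plans looks at 3, 6 and 12 months for primary and secondary objectives, using "group sequential testing methods with an O'Brien-Fleming spending function".

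**The concern.** A 95% confidence interval agrees with a P value below 0.05 only when the test is two-sided. A one-tailed 5% test pairs with a 90% two-sided interval. ANOVA F tests and chi-square tests are also non-directional. The test used for sizing is therefore not the test that 9.2 implies.

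Two things are at stake. First, a favourable result with a one-sided P between 0.025 and 0.05 would succeed on the basis used in 9.7 and fail on the criterion in 9.2. A choice of sidedness made after the data are seen would not be credible. Second, the assurance that 102 completers cover all primary and secondary metrics depends on the rows that set the size, and those rows have no margin to absorb a stricter test. In the Combined document one of them is the primary endpoint.

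**Working it through.** **Inputs (Section 9.7).** Employee Performance: 0.6 against 0.7, Variance of 20%. Total Healthcare Expenditure: 10000 against 8000, Variance of 4000. FACT-G: 70 against 85, Variance of 20. Alpha 0.05, power 80%, one-tailed, 1:1, dropout 30%.

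**Reading of the Variance column.** As standard deviations, d = 0.1/0.2 = 0.5, d = 2000/4000 = 0.5 and d = 15/20 = 0.75. Taken literally as variances, the one-sided normal formula gives 2 × 6.183 × 0.2/0.1² = 247.3, so 248 per arm, for Employee Performance, and 1 per arm for expenditure. Treating 0.6 against 0.7 as proportions gives 281 per arm. Only the standard-deviation reading leads to 51. The label is a separate error, but every power figure below depends on this reading.

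**Reproducing the plan's figure.** For a comparison of two means, n per arm = 2(z_alpha + z_beta)²/d².
- One-sided, d = 0.5: 2(1.645 + 0.842)²/0.25 = 49.5, so 50. The noncentral t gives 50.15, so **51 per arm, 102 in total**, as stated.
- Dropout: 102/0.70 = 145.7, so **146**, as stated.
- Two-sided, d = 0.5: 2(1.960 + 0.842)²/0.25 = 62.8, so 63. The noncentral t gives 63.77, so 64.

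The plan's 51 is therefore the one-sided, fixed-sample figure with no allowance for interim looks.

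**Power at 51 per arm.** The normal approximation is Φ(d√(n/2) − z), with √(51/2) = 5.050.

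| Row | Test | Normal | Noncentral t |
|---|---|---|---|
| d = 0.5 | one-sided 5% | Φ(2.525 − 1.645) = 81.1% | 80.6% |
| d = 0.5 | two-sided 5% | Φ(2.525 − 1.960) = 71.4% | 70.6% |
| FACT-G, d = 0.75 | two-sided 5% | Φ(3.787 − 1.960) = 96.6% | 96.3% |

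**Adding the looks.** I used Lan-DeMets O'Brien-Fleming spending over four looks including the final one, by numerical integration with the normal approximation. The documents do not give information fractions, so two assumptions bracket the answer: equal spacing, or information proportional to time at 3, 6, 12 and 18 months.

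| | Equal spacing | Proportional to time |
|---|---|---|
| Two-sided 5%: power, d = 0.5 | 70.5% | 70.8% |
| One-sided 5%: power, d = 0.5 | 80.1% | 80.4% |
| Two-sided: final critical z | 2.014 | 1.993 |
| Two-sided: final nominal level | 0.044 | 0.046 |
| One-sided: final critical z | 1.720 | 1.695 |
| One-sided: final nominal level | 0.043 | 0.045 |

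On the same normal scale, the looks take two-sided power from 71.4% to 70.5–70.8% and one-sided power from 81.1% to 80.1–80.4%, a cost of about one point or less. The change of sidedness takes 80.6% to 70.6%, ten points.

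**Final threshold.** If the interim boundaries were used and the final test were still made at two-sided P below 0.05, the overall error would be 5.35% (proportional to time) or 5.54% (equal spacing).

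**Employee Performance in practice.** The 70.6% assumes that all 102 completers supply a score. The endpoint concerns employed survivors, and Section 5.3 does not require employment. The documents give no employed fraction. As an illustration, 70% employed (36 per arm) gives 55% two-sided power, and 50% (about 25 to 26 per arm) gives about 42%.

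**The case against.** The only sidedness stated anywhere is one-tailed, and the alternatives are directional. If a one-sided 5% test is what the sponsor intends throughout, power for the d = 0.5 rows stays near 80% even with the looks. The rule tying P below 0.05 to the 95% interval sits under Supplementary Analysis. The Protocol's 95% wording in the primary method concerns covariate effects, and 9.3 is silent for Employee Performance. This stands: a two-sided test is an inference from the interval level and the named tests, not the documents' wording. It does not remove the inconsistency, because under a one-sided plan the 95% intervals and non-directional tests are the part that is wrong.

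A reader might also infer that the final test will be made at an unadjusted 0.05 and that type I error is uncontrolled. The documents do not say that. Section 9.6 commits to alpha spending, and the 0.05 statements appear in a supplementary analysis and a general sentence on power. What is missing is a stated final level, and the excess if none were applied is about half a point.

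Finally, the scope in the Protocol is narrow. Expenditure is exploratory there, so it falls outside the claim about primary and secondary metrics, and Employee Performance is the only primary or secondary row that sets the size.

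**Conclusion.** The inconsistency is real: the one-tailed 5% sizing in 9.7 and the 95% interval criterion in 9.2 cannot both describe the same test. On a two-sided 5% reading, the rows that set the sample size have 70.6% power at 51 per arm instead of 80.6%, almost entirely because of sidedness. In the Protocol this affects one secondary outcome, Employee Performance. In the Combined protocol and SAP it affects the primary endpoint as well.

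Two stronger readings do not hold. The Protocol's primary endpoint is not underpowered on the plan's own inputs, since FACT-G keeps about 96%. Nor do the interim looks explain the fall to 70%. The figures rest on reading Variance as a standard deviation, on all 102 completers contributing data, and, for the looks, on the assumed information fractions.

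**What to change.** State one sidedness in 9.2 and 9.3, and use it in 9.7.

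- **If two-sided 5%:** restate power at 102 completers as about 96% for FACT-G and about 70% for the d = 0.5 rows. For Employee Performance, say that this holds only if all 102 are employed and contribute data, and that power is lower otherwise. Withdraw the claim that 102 suffices for every primary and secondary metric at 80% power.
- **If one-sided 5%:** say so in 9.2 and 9.3, and replace the 95% interval, ANOVA and chi-square criteria with one-sided tests and 90% intervals.
- **In either case:** state that the final test uses the O'Brien-Fleming adjusted level instead of P below 0.05. For a two-sided test the nominal level is about 0.044 with equally spaced looks, or about 0.046 if information is proportional to time. Give the information fractions assumed.

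The cost is wording in 9.2, 9.3 and 9.7 and, on the two-sided route, a less favourable stated power for two rows. No change in enrolment is needed. For reference, fixed-sample two-sided 80% power at d = 0.5 would need 64 per arm, which is 128 completers, or 128/0.70 = 182.9, so 183 randomised (184 for equal arms).

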The evaluation of our proposed trial, which integrates live coactive coaching with a software solution for cancer survivors, demonstrates a significant favorable balance between minimal risks and anticipated benefits. The residual risks are minimized through tailored safety measures and are outweighed by the expected benefits of improved physical health, decreased symptom burden, and enhanced quality of life.

Supporting this favorable assessment, a substantial body of research not only confirms the safety of exercise but also endorses the significance of physical activity and lifestyle

changes in cancer management. This evidence base, coupled with medical endorsement of physical activity for enhancing survivor outcomes, bolsters confidence in the trial's approach.

To ensure ongoing safety and integrity, risks and benefits will be continuously assessed, adjusting protocols as necessary to safeguard participant well-being. This trial aligns with best practices in cancer treatment and reflects a commitment to advancing survivor care through evidence-based lifestyle interventions.

Section 3: TRIAL OBJECTIVES, ENDPOINTS AND ESTIMANDS

Trial Objective 1: Impact of Complement Theory's Program on Quality of Life

Clinical Question: How does participation in Complement Theory's program affect Quality of Life Scores (as measured by FACT-G) in cancer survivors compared to those receiving standard care?

- Endpoint(s): Measured through change in FACT-G scores which is designed to assess various dimensions of quality of life including pain levels and sleep quality.
- Estimand(s): The mean difference in change in scores between the intervention and control groups at specified time points during and after the intervention period.

Trial Objective 2: Effect on Employee Absenteeism

Clinical Question: How does participation in the Complement Theory program influence the number of leave days taken by employed cancer survivors due to health issues?

- Endpoint(s): Number of leave days (including sick leave, short-term disability, and long-term disability) taken by participants during the trial period.
- Estimand(s): The difference in the average number of leave days between the intervention and control groups over the trial period.

Trial Objective 3: Impact on Employee Presenteeism

Clinical Question: What is the effect of Complement Theory's program on motivation to work and performance review scores among employed cancer survivors?

- Endpoint(s):

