 - Motivation to work: Assessed through self-reported scales or questionnaires.
 - Performance review scores: Obtained from employer records or self-reported performance evaluations.
- Estimand(s): The difference in mean scores of motivation and performance reviews between the intervention and control groups over the trial period.

Exploratory Objective(s):

Impact on rates of cancer progression, and recurrence

Clinical Question: What is the effect of Complement Theory's program on progression and recurrence of prostate, lung and colorectal cancers?

- Endpoint(s):
 - Cancer progression: Measured by changes in tumor size and changes in levels of biomarkers.
 - Recurrence: Incidence of cancer recurrence.
- Estimand(s): Directional trends evaluating the difference in proportions or rates of cancer progression and recurrence between the intervention and control groups during and post-trial follow-up.

Rationale for Excluding Breast Cancer from Exploratory Objective:

- Breast cancer, in particular, exhibits a longer average timeframe for recurrence when compared to prostate, lung and colorectal cancers. This longer latency could extend beyond the scope of our study's follow-up period, making it

challenging to accurately measure the program's impact on recurrence rates within the study's duration.

- By focusing on prostate, lung and colorectal cancers, we aim to assess the program's impact on cancers with more predictable progression patterns and well-established biomarkers, enabling a clearer evaluation of the Complement Theory's potential benefits in these specific cancer populations.

Impact on Total Healthcare Expenditure

Clinical Question: Does participation in Complement Theory's 12-month Live coactive Coaching program, focusing on Exercise and Meditation and supplemented with evidence-based information on Diet, Sleep, and other lifestyle practices, adjunct to the core treatment, lead to a reduction in total healthcare expenditure for cancer survivors?

- Endpoint(s): Total healthcare expenditure, including hospitalization costs, medication expenses, outpatient visits, and any other related healthcare services that we planned and unplanned, cancer and non-cancer, over the trial period.
- Estimand(s): The difference in mean total healthcare expenditure between the intervention and control groups over a specified period (e.g., at 12 months and 18 months from baseline).

3.1 Summary of objectives, endpoints and estimands:

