8.2 Efficacy Assessments and Procedures

Improvement in Quality of Life (QoLS) as measured by FACT-G questionnaire (Trial Objective 1):

- Endpoint: Change in FACT-G scores measuring quality of life
- Assessment Procedures: Administer the above four questionnaires to assess participants' at baseline and specified time points during and after the intervention period.
- Data Collection: Obtain self-reported scores from participants on Quality of Life.

- Analysis: Calculate the mean difference in change in scores between the intervention and control groups at each time point to evaluate the impact of the intervention.

Reduction in Employee Absenteeism (Trial Objective 2):

- Endpoint: Number of leave days taken by employed cancer survivors due to health issues.
- Assessment Procedures: Track the number of leave days (sick leave, short-term disability, long-term disability) taken by participants in both groups throughout the trial period.
- Data Collection: Obtain leave records from participants' employers or self-reported information from participants.
- Analysis: Compare the average number of leave days between the intervention and control groups to assess the impact of the intervention on reducing absenteeism.

Improvement in Employee Presenteeism (Trial Objective 3):

- Endpoints: Motivation to work (self-reported scales/questionnaires), performance review scores (from employer records or self-reported evaluations).
- Assessment Procedures: Administer self-reported scales/questionnaires to assess participants' motivation to work and obtain performance review scores from employer records or self-reported evaluations.
- Data Collection: Collect self-reported data on motivation to work and obtain performance review scores from participants and their employers.
- Analysis: Compare the mean scores of motivation and performance reviews between the intervention and control groups to evaluate the impact of the intervention on enhancing presenteeism.

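### Protocol 9.7 claims 80% power for every primary and secondary metric at 102 completers, but Employee Performance, the one such row needing all 102, is measured only in employed survivors and no allowance is made for that

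*Protocol*

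**What the plan says.** Protocol 9.7 sizes each metric separately with "alpha as 0.05 and power of 80% for the one-tail test at enrollment ratio = 1", takes the largest result, and concludes that a "sample of size of 102 is powerful enough for the analysis to cover 100% of primary and secondary metrics". It expects that follow-up "will lead to around 30% drop-offs, we decided a final sample size of 146 (73 control, 73 test"), so that "102 (51 control, 51 test") remain after dropout. It then repeats that significance would be reached "with respect to 100% of primary and secondary metrics". Dropout is the only allowance made.

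The Protocol's primary and secondary rows are:

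| Row | Control vs test | Stated spread | Stated N |
|---|---|---|---|
| FACT-G (primary) | 70 vs 85 | 20 | 42 |
| Attitude towards work | 2 vs 4 | 1.5 | 16 |
| Employee Performance | 0.6 vs 0.7 | 20% | 102 |
| Working Hours | 30 vs 40 | 10 | 28 |
| Vacation Days | 0.5 vs 0.3 | 0.15 | 16 |

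Total Healthcare Expenditure also shows 102, but it is exploratory in this Protocol.

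Section 3, Trial Objective 3, asks about "motivation to work and performance review scores among employed cancer survivors"; the summary table in 3.1 repeats that population. The estimand is "The difference in mean scores of motivation and performance reviews between the intervention and control groups over the trial period". For data collection, section 8.2 says to "obtain performance review scores from participants and their employers"; sections 3 and 8.2 also accept self-reported evaluations. Sections 5.3 and 5.4 contain no employment criterion, and the age range is 21 and above with no upper limit. Section 8.1 records at baseline whether a participant is on short- or long-term disability.

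**The concern.** The row that sets 102 among the primary and secondary metrics can be observed only in a subset of participants, yet 9.7 counts every completer towards it. The dropout allowance brings 146 down to exactly 102, which leaves nothing for participants without a job or without a score.

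A reader of 9.7 would take Employee Performance as covered at 80% power whatever share of the sample works. If the employed share is lower than the analysis can absorb, a null result on this metric would carry less information than 9.7 implies.

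**Working it through.** **Inputs.** From Protocol 9.7: one-tailed alpha 0.05, power 80%, 1:1 allocation, Employee Performance 0.6 vs 0.7 with spread 0.20, dropout 30%. The employed share is not in the documents; a range is assumed.

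**Reproducing 102 and 146.** Reading the spread as an SD, d = (0.7 − 0.6)/0.20 = 0.5. A one-tailed two-sample t-test needs 50.15 per arm, so 51 per arm, or 102. Inflation for dropout: 102/0.70 = 145.7, so 146. Check: 0.30 × 146 = 43.8, so 44 lost, and 146 − 44 = 102. Both figures match exactly. If 0.20 were a true variance, d = 0.1/√0.20 = 0.224 and 248 per arm would be needed, so the table is using SDs under a variance label.

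**Slack.** At d = 0.5, power is 80.6% with 51 per arm and 79.9% with 50. There is effectively none.

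**Power by employed share.** Unadjusted one-tailed t-test, d = 0.5. The middle column takes 51 completers per arm times the share. The last takes all 73 randomised per arm times the share, the limiting case in which every participant who drops out has still supplied usable scores.

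| Assumed share employed and scored | n per arm and power, from 51 | n per arm and power, from 73 |
|---|---|---|
| 100% | 51.0: 80.6% | 73.0: 91% |
| 90% | 45.9: 77% | 65.7: 89% |
| 80% | 40.8: 72% | 58.4: 85% |
| 60% | 30.6: 61% | 43.8: 75% |
| 50% | 25.5: 55% | 36.5: 68% |

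With no loss at all, 102/146 = 70% employed would be enough for 102 scored participants.

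**What adjustment could add.** Correlations are assumed; n per arm is 51 times the share.

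- Baseline plus one follow-up score: effective d = 0.5/√(1 − r²). At r = 0.5 this is 0.577, and power at 80/60/50% employed is 83/72/65%. Reaching 80% takes 38 per arm (38/51 = 75%). At r = 0.7, power is 93/86/79% and 26 per arm are needed (51%).
- Baseline plus the mean of k = 4 follow-up scores, with compound symmetry and a constant effect: d = 0.5/√((1 + (k − 1)r)/k − r²). At r = 0.5 this is 0.816, power is 98/94/89%, and 20 per arm are needed (39%).

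These gains shrink if 0.20 is already the SD of a change score.

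**Other primary and secondary rows.** FACT-G, d = 15/20 = 0.75: 98% power at 51 per arm, and not restricted to employed survivors. Attitude towards work and Vacation Days, d = 1.333: 8 per arm, or 8/51 = 16% of completers. Working Hours, d = 1.0: 14 per arm, or 14/51 = 27%.

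**Table recheck.** With the spread read as SD, 14 of the 17 Protocol rows reproduce. The exceptions are:

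| Row | d | Computed per arm | Stated per arm |
|---|---|---|---|
| FACT-G | 0.75 | 23 (80.5%; 21 gives 77.2%) | 21 |
| Prescription expenditure (exploratory) | 50/80 = 0.625 | 33 | 40 |
| Planned hospital visits (exploratory) | 0.25/0.1 = 2.5 | 3 | 5 |

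The table itself gives 23 per arm for Cancer Progression, where d = 0.03/0.04 is also 0.75.

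**The case against.** The best counter-argument is that 9.7's unadjusted comparison is not the planned analysis. Section 9.3 plans mixed-effects models of performance scores over time. Section 6.1 schedules the performance review at baseline, in odd-numbered weeks of the active phase, and every 30 days in months 7 to 18. Section 9.7 attributes the 30% loss to the long follow-up, so someone lost late may already have many scores. The usable number per arm therefore lies between 51 and 73 times the employed share, and adjustment for baseline or repeated scores can add more. This stands: no particular power deficit can be asserted. It does not rescue the sentence in 9.7, which invokes no such gain and gives no employed share, number of scores or correlation. The upper limit is not assured either, because the endpoint is not tied to a time point and losses may come early.

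Two further objections also stand. Self-reported evaluations are accepted, so missing employer records alone need not remove a score. In the Combined protocol and SAP, Total Healthcare Expenditure is a primary row that needs 102 without any restriction to employed survivors. The statement that Employee Performance alone sets 102 is therefore true only of the Protocol. It also follows that an unchanged 102 under the Combined document's narrower age range of 21 to 64 says little about how employment was treated.

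A reader might object that 9.7 is one-tailed while the later sections are not. The alternatives in 9.2 and 9.3 are already directional, in favour of the intervention, so there is nothing to correct on that score.

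**Conclusion.** The unconditional coverage claim is not supported on 9.7's own basis. With 102 completers, Employee Performance has 80% power only if essentially all of them are employed and scored. At assumed shares of 90 to 50%, unadjusted power runs from 77% down to 55% with 51 completers per arm. The planned model may recover some or all of the loss, so the true shortfall is undetermined. The wording defect is certain; its effect on power is not.

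A reader might infer that the trial is too small, or that 146 must rise by dividing by the employed share. The documents do not support that. The primary endpoint has 98% power at 51 per arm on the stated inputs, the other work-related metrics need at most 27% of completers, and the employed share is unknown. Nor do the table errors disturb the sizing: none of them changes 102 or 146. The point affects the stated power of one secondary metric and should be fixed in the text.

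**What to change.** 1. In both coverage sentences of Protocol 9.7, except Employee Performance and keep the claim for the other primary and secondary metrics. Suggested addition: *Under the unadjusted one-tailed comparison that reproduces the table, 51 per arm gives 80% power for Employee Performance only if all 102 completers are employed and have a performance score. The expected number of employed, scored participants is [sponsor to state]; power under the planned mixed model is [value], assuming [employed share, number of scores, correlation].*
2. In the table, relabel the spread column as SD. Correct FACT-G to 46 (23 per arm). Correct or explain prescription expenditure and planned hospital visits.
3. In section 9.7 of the Combined protocol and SAP, qualify Employee Performance in the same way, while recognising that Total Healthcare Expenditure also sets 102 there.

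The cost is text and table edits, plus an employed share and model assumptions that the sponsor must commit to. The stated power for one secondary metric becomes conditional and may be lower. No added enrolment is needed.
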